### **9.3.2 Life-Style**

Subjects will be instructed to have moderate-intensity physical activity (e.g., 30 min walking every day) during the study.

Subjects will be instructed to continue, without change, their smoking habits during the study.

The compliance of the subjects with the proposed life-style will be assessed by the Investigator's Team at each visit during the study.

---

## **10. STUDY DURATION**

### **10.1 Study Duration per Subject**

#### **10.1.1 Screening Period**

The maximum duration of the screening period is 21 days.

#### **10.1.2 Baseline Period**

The duration of the baseline period is 1 day.

#### **10.1.3 Treatment Period**

The duration of the double-blind treatment period (active product versus placebo) is 168 days with a visit window of 2 or 3 days (see Section 12.1).

#### **10.1.4 Post-Treatment Follow-up Period**

The duration of the follow-up period is 28 days with a visit window of 3 days for Visit 14 but no visit window for Visit 13 (see Section 12.1).

## **10.2. Total Study Duration**

The total study duration will be approximately 2 years (including approximately 1 and half years for enrollment). The start date is expected to be during the second half of 2014 and the end date during the first half of 2017.

## **11. STUDY ENDPOINTS**

When hydrated, Gelesis100 has some weight by itself. At any time following the first day of Gelesis100 administration, subjects may accumulate up to 1 kg of hydrated Gelesis100 in their gastrointestinal tract. Therefore, it is likely to observe an initial weight gain during the first days or weeks of treatment until the extra weight is counter-balanced by the weight loss caused by Gelesis100. An interval of 2 days is required for any remaining Gelesis100 to be eliminated from the gastrointestinal tract. For these reasons, to ensure that the weight of Gelesis100 does not mask the true amount of weight loss, the end of treatment assessment of body weight and weight-related parameters will be performed on Day 171, approximately 60 h after the last administration of Gelesis100.

### **11.1 Effectiveness Endpoints**

#### **11.1.1 Co-Primary Endpoints**

- Body weight (percent change from baseline to Day 171)
- Body weight responders ( $\geq 5\%$  weight loss from baseline to Day 171)

---

### **11.1.2 Secondary Endpoints**

- Plasma glucose status (normal, impaired, diabetic) (change from baseline to Day 171)
- Plasma glucose (percent change from baseline to Day 171)
- HOMA-IR (percent change from baseline to Day 171)
- HbA1c (change from baseline to Day 171)
- BMI (change from baseline to Day 171)

### **11.1.3 Tertiary Endpoints**

- Body weight responders ( $\geq 10\%$  weight loss from baseline to Day 171)
- Estimated excess body weight (percent change from baseline to Day 171)
- Body weight status (normal, overweight, obese) (change from baseline to Day 171)
- Waist circumference (change from baseline to Day 171)
- Serum insulin (percent change from baseline to Day 171)
- Serum C-reactive protein (CRP) (change from baseline to Day 171)
- Serum total cholesterol (percent change from baseline to Day 171)
- Serum LDL cholesterol (percent change from baseline to Day 171)
- Serum high-density lipoprotein (HDL) cholesterol (percent change from baseline to Day 171)
- Serum total cholesterol/HDL cholesterol ratio (change from baseline to Day 171)
- Serum triglycerides (percent change from baseline to Day 171)
- Supine and standing SBP and DBP (change from baseline to Day 171)
- Food intake (change from baseline to Day 169)
- Food habits (change from baseline to Day 169)
- Satisfaction (overall impression on Day 169)
- Impact of weight on quality of life (IWQOL) (change from baseline to Day 171) (at selected sites)

The secondary and tertiary effectiveness endpoints are for supportive purposes only.

## **11.2 Safety Endpoints**

### **11.2.1 Adverse Events**

- All AEs and SAEs (including ADEs and SADEs)

### **11.2.2 Physical Examination**

- Full physical examination (excluding pelvic and rectal examination)

### **11.2.3 Vital Signs**

- Supine and standing SBP and DBP
- Supine and standing heart rate

### **11.2.4 Laboratory Tests**

- Hematology including hemoglobin, hematocrit, red blood cell count, reticulocyte count, white blood cell count with differential, and platelet count
- Blood chemistry including plasma glucose and serum sodium, potassium, chloride, calcium, phosphorous, magnesium, blood urea nitrogen, creatinine, uric acid, total cholesterol, LDL cholesterol, HDL cholesterol, triglycerides, total protein, albumin, total bilirubin, alkaline phosphatase, lactate dehydrogenase, alanine aminotransferase, aspartate aminotransferase, and gamma glutamyltransferase
- Vitamins including vitamin A, vitamins B1, B2, B6, B9, and B12, vitamin D, and vitamin E (vitamins will be measured in approximately 60 subjects from the sites of Czech Republic and the site of Rome, Italy)

## **11.3 Assessment Methods**

All the assessments, unless otherwise specified, will be performed in the morning (between approximately 7 am and 10 am), before product intake, on fasting subjects (10 to 12-h fast) with no moderate or intense physical activity within the past 12 h. Physical examination, dietary interview, and electrocardiogram (ECG) can be performed at any time during the day regardless of food or investigational product intake.

### **11.3.1 Clinical**

#### ***11.3.1.1 Physical Examination***

A full physical examination (excluding pelvic and rectal examination) will be performed by the Investigator. The physical examination will cover the following areas:

- general appearance
- eyes
- ears, nose, throat
- neck
- respiratory
- cardiovascular
- endocrine
- hepatic
- gastrointestinal
- genitourinary
- peripheral vascular
- neurological
- musculoskeletal
- extremities

---

- lymphatic
- dermatological
- allergies
- psychiatric

#### ***11.3.1.2 Body Weight***

Body weight should be obtained with the subject wearing undergarments or very light clothing and no shoes, and with an empty bladder. The same scale should be used throughout the study. The use of a balance-beam scale is recommended. If a digital scale is used, testing with standard weights is of particular importance. The scale needs to be calibrated within 12 months prior to the first Screening Visit and its precision should be verified every 4 months after the first Screening Visit. The floor surface on which the scale rests must be hard and should not be carpeted or covered with another soft material and the scale must not be moved during the entire duration of the study. The scale should be balanced with both weights at zero and the balance bar aligned. The subject should stand in the center of the platform as standing off-center may affect the measurement. The weights are moved until the beam balances (the arrows are aligned). The weight is read and recorded. Self-reported weights are not acceptable. Subjects must not read the scale themselves.

#### ***11.3.1.3 Waist Circumference***

Waist circumference should be measured according to the established methods. It is taken at the midpoint between the lower rib margin and the iliac crest. The circumference should preferably be measured on subjects while they are semi-clothed (i.e., waist uncovered with the subjects wearing underclothes only). If it is not possible to follow this procedure, the alternative is to measure the circumference on subjects without heavy outer garments with all tight clothing, including the belt, loosened and with pockets emptied. Subjects should stand with their feet close together (no more than 15 cm apart) with their weight equally distributed on each leg. Subjects should be asked to breathe normally and at the time of the reading of the measurements asked to breathe out gently. This will prevent subjects from contracting their muscles or from holding their breath. A plastic metric tape should be used. The length of the tape should be checked before starting the study and the length should be re-checked against a standard measure at least once a month and the tape should be replaced as appropriate. The two sides of the tape should be differently colored or have a scale only on 1 side. If the tape is uniformly colored, with reading on both sides, 1 side should be blanked out. The tape should be held firmly and its horizontal position should be ensured. The tape should be loose enough to allow the recorder to place 1 finger between the tape and the subject's body. The importance of the tightness of the tape should be emphasized. It is recommended that the observer sits beside the subject while the readings are taken. Three measurements will be performed and recorded.

#### ***11.3.1.4 Blood Pressure***

SBP and DBP will be measured using a calibrated device. The device will be a mercury sphygmomanometer with a cuff appropriate to the subject's arm girth (obesity cuff). If not available, another device may be used which is calibrated carefully in proportion to a

---

mercury sphygmomanometer. Aneroid manometer is not recommended. The calibration of the device will be according to the site-specific guidelines and requirements. The same model of device will be used for each subject throughout the study. Blood pressure should be measured under standardized conditions, on the same arm. Both SBP and DBP should be recorded. The disappearance of sound (Korotkov phase V) should be used for the diastolic reading. Blood pressure should be measured in both supine position (after the subject has rested comfortably for at least 5 min) and standing position (after 2 min). At the Screening Visit, supine blood pressure should be checked in both arms on two consecutive readings separated by 2 min. The arm with the higher SBP will be determined at this visit based on the mean of two consecutive readings, and blood pressure should be measured in this arm throughout the study. At each other visit, two readings of supine blood pressure separated by 2 min should be recorded.

#### **11.3.1.5 Heart Rate**

Heart rate (pulse) will be measured over 1 min at the time of the second measurement of supine blood pressure and at the time of the measurement of standing blood pressure and the results will be recorded.

#### **11.3.1.6 Electrocardiogram**

ECG will be obtained using a 12-lead cardiograph. The maintenance of the device will be according to the site-specific guidelines and requirements. ECG will be performed after a 15-min rest in supine position.

#### **11.3.1.7 Binge Eating Disorder**

The questionnaire on eating and weight patterns-revised (QEWP-R) abbreviated version will be used to identify subjects with binge eating (Appendix 1). Subjects are excluded from enrollment if the answer to question 11 is yes except if they are considered as mild binge eaters according to the Investigator's assessment.

#### **11.3.1.8 Food Intake**

Food intake will be assessed by food diary. The diary will include all the meals consumed during any 2 consecutive weekdays and 1 weekend day before the visit. The assessment will include global food intake (including fluid intake), carbohydrate intake, fat intake, protein intake, and fiber intake.

#### **11.3.1.9 Food Habits**

Food habits will be assessed by a questionnaire (Appendices 2 and 3).

#### **11.3.1.10 Satisfaction**

A questionnaire will record the thoughts of the subjects regarding the investigational product (Appendix 3). The questionnaire will be completed by the subjects at the last treatment visit.

#### **11.3.1.11 Impact of Weight on Quality of Life**

The IWQOL questionnaire will ask subjects at selected sites about the impact of weight on their quality of life (Appendix 4).

---

### **11.3.1.12 Adverse Events**

All AEs and SAEs will be recorded (see Section 13).

## **11.3.2 Biological**

### **11.3.2.1 Blood Parameters and Genomic Tests**

Blood samples will be collected by venipuncture and shipped to the local or central laboratory as per laboratory instructions (provided in a laboratory manual).

Insulin resistance will be measured by HOMA-IR (15), which is calculated by multiplying fasting serum insulin ( $\mu$ U/mL) by fasting plasma glucose (mmol/L) and dividing by 22.5.

Serum amylase results will be reported as total serum amylase and pancreatic serum amylase.

Genomic tests will include the analysis of copy number variation of AMY1 gene (gene encoding salivary amylase) and additional analysis of several genes involved in obesity and type 2 diabetes (BDNF, CAPN10, FTO, KCNJ11, LEPR, MC4R, NEGR1, NPC1, PCSK1, PPARG, SH2B1, SLC16A13, and TCF7L2 genes). Blood samples for the extraction and analysis of deoxyribonucleic acid will be shipped to the central laboratory as per laboratory instructions. The results of genomic tests together with the results of serum amylase will be correlated to weight-related and metabolic parameters at baseline and their evolution during the study, in different populations.

The total blood requirement per subject for all blood samplings will be approximately 70 mL over approximately 31 weeks. An additional 25 mL of blood per subject will be drawn during the entire study at sites where vitamins should be measured and 5 mL of blood per subject will be drawn at a single visit for genomic tests.

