## 2. STUDY FLOW CHART

Period (duration)	Screening (≤ 21 days)	Baseline (1 day)	Double-blind treatment (168 days)												Follow-up (28 days)
Visit	1	2	3	4	5	6	7	8	9	10	11	12	13 I	14	
Day	-21 to -1	0	8	15	29	43	57	71	85	113	141	169	171	197	
Week	-3 to 0	0	1	2	4	6	8	10	12	16	20	24	25	28	
Informed consent		X													X J
Demography, height		X													
Menopausal status, smoking status, medical history		X													
Physical examination		X	X												X
Weight, waist circumference, vital signs (blood pressure, heart rate)		X	X	X	X	X	X	X	X	X	X	X	X	X	X
Dietary interview		X	X	X	X	X	X	X	X	X	X	X	X	X	X
Binge eating disorder		X													
Food habits before treatment				X											
Serum pregnancy test A		X	X												X
Urine pregnancy test A , serum amylase B , genomic tests C			X												
Electrocardiogram, urine drug screen		X													
TSH D		X													X
Plasma glucose		X	X	X	X	X									X
Serum insulin			X	X	X										X
IWQOL E			X												X
Serum CRP, vitamins F			X												X
Serum albumin		X	X		X	X									X
Hematology, blood chemistry, HbA1c		X	X												X
Food intake G			X			X		X		X	X	X	X	X	
Food habits and satisfaction after treatment															X
Concomitant medication recording, AEs recording		X	X	X	X	X	X	X	X	X	X	X	X	X	X
Randomization			X												
Gelesis100/placebo accountability				X	X	X	X	X	X	X	X	X	X	X	
Gelesis100/placebo dispensed H			X	X	X	X	X	X	X	X	X	X	X	X	

AFemales of childbearing potential only. BAt any of the Visits 2, 3, 4, 5, 9, or 13. CAt any of the Visits 2, 3, 4, 5, 9, or 13 (tests not mandatory). DThe assessment of Week 12 is for subjects on replacement therapy with thyroid hormones or preparations only. EAt selected sites. FAt selected sites (vitamins include vitamin A, vitamins B1, B2, B6, B9, and B12, vitamin D, and vitamin E). GFood diary on 2 consecutive weekdays and 1 weekend day before the visit. HAdministration begins on Day 1 and continues through Day 168, before lunch and dinner. ILast visit if entering extension study. JIf entering extension study.

---

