### **12.2.2 Visit 2 (Baseline Visit; Day 0)**

- Physical examination
- Weight
- Waist circumference
- Vital signs (supine and standing blood pressure and heart rate)
- Dietary interview (dietary prescription)
- Food intake
- Food habits

---

- IWQOL
- Serum amylase (blood can be collected at any of the Visits 2, 3, 4, 5, 9, or 13)
- Genomic tests (blood can be collected at any of the Visits 2, 3, 4, 5, 9, or 13) (tests not mandatory)
- Serum pregnancy test (women of childbearing potential only)
- Urine pregnancy test (women of childbearing potential only) (test performed at the Investigator's site)
- Serum insulin
- HbA1c
- Serum CRP
- Hematology
- Blood chemistry
- Vitamins
- Concomitant medication record
- Randomization
- Dispensation of study product (administration begins the following day)
- AEs and SAEs records

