## **15.2 Baseline and Visit Windows**

Baseline for a given parameter or endpoint is defined to be the last observation (obtained at either the Screening or Baseline Visit) taken before the first study product administration. The study visits and visit windows are Days  $8 \pm 2$ ,  $15 \pm 2$ ,  $29 \pm 2$ ,  $43 \pm 2$ ,  $57 \pm 2$ ,  $71 \pm 2$ ,  $85 \pm 2$ ,  $113 \pm 3$ ,  $141 \pm 3$ ,  $169 \pm 3$ , 171, and  $197 \pm 3$ .

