### **15.7.5 Subgroup Analysis**

Several subgroup analyses will be conducted for the stratification factors as well as the pre-specified secondary endpoints. Subgroup analyses will also be performed based on the results of serum amylase and genomic tests. The detail of these subgroup analyses will be presented in the SAP.

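### Does letting serum amylase be sampled before or during treatment undermine its planned correlation with change over the study?

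*Combined protocol and SAP*

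**What the plan says.** Serum amylase may be drawn once within a wide window. The flow chart footnote (Section 2) reads "At any of the Visits 2, 3, 4, 5, 9, or 13", and Section 12.2.2 repeats the list. The nominal days are 0, 8, 15, 29, 85 and 171.

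On dosing, the flow chart states "Administration begins on Day 1 and continues through Day 168, before lunch and dinner". On the endpoint, Section 11 states that "the end of treatment assessment of body weight and weight-related parameters will be performed on Day 171", which is Visit 13.

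Two uses of amylase are planned. Section 11.3.2.1 says that "serum amylase will be correlated to weight-related and metabolic parameters at baseline and their evolution during the study". Section 15.7.5 adds "Subgroup analyses will also be performed based on the results of serum amylase and genomic tests", followed by "The detail of these subgroup analyses will be presented in the SAP". Neither section names a sampling visit.

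Section 15.2 defines the baseline of any parameter as the last observation "taken before the first study product administration". Sections 15 and 15.8 leave detailed methods and data conventions to a separate SAP, to be approved before database lock. That document is not part of the supplied text.

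**The concern.** Five of the six permitted visits fall after dosing has begun, and one falls on the day the endpoint weight is taken. The same window covers the genomic tests, where it is harmless because inherited genotype does not change with treatment. Serum amylase is a circulating level and could change.

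If weight loss or the product shifts amylase, a sample taken late carries part of the outcome with it. Its correlation with change over the study could then be read as a predictor of response when it is partly a consequence. Subgroups formed on such a value would be defined after randomisation, which is normally avoided. At stake is the interpretation of one biomarker correlation and one set of subgroups, not the co-primary results.

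**Working it through.** **1. Timing.** With first dosing on Day 1:

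| Visit | Day | Relative to dosing | Day/171 |
|---|---|---|---|
| 2 | 0 | before | 0 |
| 3 | 8 | after | 0.05 |
| 4 | 15 | after | 0.09 |
| 5 | 29 | after | 0.17 |
| 9 | 85 | after | 0.50 |
| 13 | 171 | after | 1.00 |

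The factual premise is correct. In Section 11.3.2.1 the words about baseline describe the weight and metabolic parameters, not the amylase sample, so they do not settle the timing. Section 15.2 does prevent a sample from Visit 3 or later being presented as baseline amylase.

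**2. Size of any distortion.** The plan gives no figure for how amylase behaves, so the inputs are partly assumed. From Section 15.4: 161 completers per arm, a 4.5-point difference and SD 5. Assumed: Visit 2 amylase is unrelated to outcome; amylase on day d is unit-variance noise plus f·b·(weight loss/5), with linear drift f = d/171; and b is set so that the Day 171 within-arm correlation ρ is 0.2, 0.3 or 0.5, that is b = ρ/√(1 − ρ²) = 0.204, 0.314 or 0.577.

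With the arms pooled, the variance of (weight loss/5) is V = 1 + (4.5/5)²/4 = 1.2025. For a single sampling visit, r = f·b·√V / √(1 + f²b²V).

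- Visit 13, ρ = 0.3: 0.3145 × 1.0966 / √(1 + 0.0989 × 1.2025) = 0.3449/1.0578 = 0.33.
- Visit 9, ρ = 0.3: f = 85/171 = 0.497, so 0.1714/√(1 + 0.0294) = 0.17.

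Simulation (4,000 trials per scenario) agrees and covers mixed schedules:

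| Sampling pattern (linear drift) | ρ = 0.2 | ρ = 0.3 | ρ = 0.5 |
|---|---|---|---|
| All at Visit 2 | 0.00 | 0.00 | 0.00 |
| All at Visits 3–5 | 0.02 | 0.04 | 0.06 |
| Half at Visit 2, rest spread | 0.04 | 0.06 | 0.11 |
| Even over six visits | 0.07 | 0.10 | 0.18 |
| All at Visit 9 | 0.11 | 0.17 | 0.30 |
| All at Visit 13 | 0.22 | 0.33 | 0.53 |

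The even-spread row becomes 0.10/0.15/0.26 if drift levels off early, and 0.19/0.27/0.46 if the full shift is present by Day 8. If amylase does not move (ρ = 0), every entry is zero. The Visit 13 row is close to the assumed ρ handed back, slightly enlarged by pooling the arms.

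**3. Subgroups.** Splitting at the median, with an even spread and linear drift, the true 4.5-point treatment effect is estimated at 4.4 to 4.5 in both halves. Across the linear-drift scenarios an interaction test at 5% rejects 4.5 to 5.7% of the time. Even with all samples at Visit 13 and ρ = 0.5, the effect falls to about 3.8 in both halves alike (3.81 and 3.78), so no false contrast between subgroups appears.

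**4. Price of allowing only Visit 2 samples.** The correlation detectable with 80% power (two-sided 5%, Fisher z) is tanh(2.80/√(n − 3)).

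- n = 322: tanh(2.80/√319) = 0.16.
- Visits 2–5 under an even spread, n = 322 × 4/6 ≈ 215: tanh(2.80/√212) = 0.19.
- Visit 2 alone under an even spread, n = 322/6 ≈ 54: tanh(2.80/√51) = 0.37.
- n = 40: tanh(2.80/√37) = 0.43.

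The list of changes at the front of the plan shows amylase as an addition to the protocol, so subjects already past Visit 2 could be sampled only later. The Visit 2 count could be smaller than an even spread implies.

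**The case for a change.** The strongest case for a change is that the fix is only wording. The protocol or SAP could make Visit 2 samples the main analysis and show later ones separately, with nothing discarded and no new blood drawn. The rule could be set before unblinding. The deferral in Section 15.7.5 covers subgroups specifically, while Section 11.3.2.1 makes no such deferral for the correlation, which is where the distortion would lie. If amylase does follow weight loss, a pooled correlation of 0.1 to 0.2 could be mistaken for a predictive signal.

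Part of this stands. The supplied text does not say how sampling visit is handled, and a pooled correlation that includes many Visit 9 and Visit 13 samples should not be read as prediction. The rest is weaker. Sections 15 and 15.8 defer methods and data conventions generally, and the choice of sample for a correlation is such a detail. Section 11.3.2.1 promises a correlation, not a prediction; an association that arises because weight loss moves amylase is misleading only if read as predictive. The remedy also has a real cost: it removes Visits 3–5 from the main analysis, where the induced correlation is 0.02 to 0.06 under linear drift (0.06 to 0.16 if drift levels off early), and may leave too few subjects for more than description.

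**Conclusion.** No change to the plan follows. The sampling window is open as described, but this is unstated analytical detail rather than a decision to pool pre-dose and post-dose samples. The harm depends on amylase changing with treatment or weight loss, which the documents neither state nor imply. On the assumptions above, the induced correlation is 0.07 to 0.18 for an even spread with linear drift, up to 0.46 in the most adverse drift pattern examined for that spread, and zero if amylase is stable. Subgroup treatment effects are essentially untouched under the even spread with linear drift.

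The wide window is a fair trade-off for a marker added by amendment: it gains subjects at some cost in clarity of timing. Restricting to Visit 2 would raise the detectable correlation from 0.16 to about 0.37, a choice on which statisticians could reasonably differ. Amylase appears in no endpoint list in Section 11, and that section describes even the secondary and tertiary endpoints as supportive only. An analyst writing the SAP would be expected to tabulate the sampling visit, show the correlation with change by visit and arm, and describe post-dose values as post-randomisation. All of that is possible under the present text.
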